3. STUDY DESIGN

3.1 DESCRIPTION OF THE STUDY

This is an open-label, phase I/II trial, which will assess the safety, tolerability and efficacy of a treat and extend management protocol for DME. Eyes which meet screening criteria will be enrolled into one of three treatment groups: (1) monthly intravitreal injections of 0.3 mg ranibizumab (Monthly Cohort, 30 eyes); (2) monthly intravitreal injections of 0.3 mg ranibizumab for 4 visits, followed by a “Treat and Extend” protocol based on pre-specified criteria of disease activity (T-REX cohort, 60 eyes); (3) monthly intravitreal injections of 0.3 mg ranibizumab for 4 visits combined with adjunctive Guided focal Laser photocoagulation to microaneurysms at week 4 and then every 3 months if leakage is present on fluorescein angiography, followed by a treat and extend protocol based on pre-specified criteria of disease activity (GILA cohort, 60 eyes).

Randomization Scheme:

All eyes which satisfy all inclusion/exclusion criteria will be randomized 1:2:2 into the Monthly:TREX:GILA Cohorts.

3 Treatment arms:

1. Monthly Cohort (30 eyes): Monthly intravitreal injections of 0.3 mg ranibizumab for 36 months, unless they meet pre-specified criteria for PRN treatment (indicated below). Treatment will begin at Day 0 and

subsequent study visits should be scheduled to occur every 28 (± 7) days relative to the date of the first injection. Dosing should not occur earlier than 21 days after previous treatments.

Starting at week 104, study eyes will have the opportunity to undergo treatment on a pro re nata (PRN) basis. Thus, eyes who have a central subfield thickness (CST) ≤ 325 microns at the week 104 visit, will not be given treatment at week 104. Eyes will continue to be seen every 4 weeks and will be given an intravitreal injection of ranibizumab 0.3 mg only if the CST is > 325 microns. Eyes will also receive treatment if there is a > 5 letter loss due to DME (compared to the vision at week 104), regardless of thickness on OCT.

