3. GILA Cohort (60 eyes): Monthly intravitreal injections of 0.3 mg ranibizumab for four visits combined with Guided LAser (GILA) photocoagulation to all microaneurysms in the area of DME at the second visit (Week 4). Fluorescein angiography is to be repeated approximately every 3 months (the first visit that occurs ≥ 90 days from the preceding fluorescein angiography visit). Guided laser will be repeated at those visits if leakage is present from microaneurysms.

If the central foveal thickness is $\leq 325 \mu\text{m}$ at Week 12 then the baseline retinal thickness will be recorded, the eye will receive 0.3 mg ranibizumab, and the study eye will begin the extension phase of the study. In the extension phase, appropriate changes to the treatment interval with 0.3 mg ranibizumab (i.e. extend, maintain, reduce) will be made based on pre-specified SD-OCT criteria (SEE TREATMENT INTERVAL DETERMINATION). Treatment is rendered at every visit, no earlier than 7 days before the target date and no later than 7 days after the target date, but the time between visits is individualized based on each subject's response to treatment. Dosing should not occur earlier than 21 days after previous treatments.

If the central foveal thickness is $> 325 \mu\text{m}$ at week 12, then the patient will continue to receive monthly intravitreal injections of 0.3 mg ranibizumab and possible guided laser photocoagulation, approximately every 3 months until the central foveal thickness is $\leq 325 \mu\text{m}$. Once the central foveal thickness is $\leq 325 \mu\text{m}$, then the study eye will begin the extension phase of the study.

Starting at week 104, study eyes will have the opportunity to undergo treatment on a pro re nata (PRN) basis. Thus, eyes who have a central subfield thickness (CST) ≤ 325 microns at the week 104 visit, will not be given treatment at week 104. Starting at week 104, eyes will be seen every 4 weeks and will be given an intravitreal injection of ranibizumab 0.3 mg only if the CST is > 325 microns. Eyes will also receive treatment if there is a > 5 letter loss due to DME (compared to the vision at week 104), regardless of thickness on OCT.

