If at any point in the study period, the study eye has improved more than 20% from the primary baseline thickness for three consecutive visits and there is less than 50 microns of variability in central foveal thickness between these visits, then a "Secondary Baseline" retinal thickness will be established. This "Secondary Baseline" retinal thickness will then be used for treatment interval determinations from that point forward. If the study eye has improved more than 20% from the secondary baseline thickness for three consecutive visits and there is less than 50 microns of variability in central foveal thickness between these visits, then a "Tertiary Baseline" retinal thickness will be established. This "Tertiary Baseline" retinal thickness will then be used for treatment interval determinations from that point forward.

Treatment Interval Determination For TREX and GILA Cohorts:

Starting at Week 12, if the central foveal thickness is $\leq 325 \mu\text{m}$, then the following re-treatment criteria will be applied at all visits. Eyes with central foveal thickness $> 325 \mu\text{m}$ at week 12 will continue to receive monthly injections of 0.3 mg ranibizumab until the central foveal thickness is $\leq 325 \mu\text{m}$, at which time the following re-treatment criteria will be applied at all visits. Eyes in the GILA cohort will continue to receive guided laser photocoagulation to microaneurysms every 3 months if leakage is present on fluorescein angiography. This treatment interval determination will continue up to week 104.

Extend Interval (by 2 weeks):

1. If the central foveal thickness on SD-OCT is within $\leq 10\%$ thicker or thinner compared to baseline (primary, secondary, or tertiary baseline) retinal thickness.

Maintain Interval:

1. If the central foveal thickness is between $> 10\%$ thicker and $\leq 20\%$ thicker from the baseline retinal thickness (primary, secondary or tertiary baseline) OR
2. If the central foveal thickness is $> 10\%$ thinner from baseline retinal thickness (primary, secondary or tertiary baseline).

Reduce Interval (by 2 weeks):

1. If the central foveal thickness is $> 20\%$ thicker from baseline retinal thickness (primary, secondary or tertiary baseline).

Reduce Interval to 4 weeks:

1. If there is a loss of more than 15 letters from best previous ETDRS vision, due to DME.

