Study eyes which have not met criteria allowing them to extend to greater than or equal to 6 weeks for two consecutive visits by the week 52 (hard endpoint) visit will receive a series of three intravitreal injections of ranibizumab 0.3 mg every 4 weeks regardless of SD-OCT measurement. This series of three injections every 4 weeks will begin at the first treatment visit that occurs after the 52 week hard endpoint visit. The study eye will resume treatment interval determinations based on the pre-specified criteria at the time of the third monthly intravitreal injection.

The interval between study injections will not exceed 12 weeks in year one of the study. The interval between study injections can be extended to, but not more than, 16 weeks in year two of the study.

Enrolled subjects will have ETDRS BCVA, complete ophthalmic examination and SD-OCT evaluation using Spectralis machines at each visit. Fluorescein angiography will be done in the Monthly and TREX Cohorts at baseline (screening visit) and again at week 12, week 52, and week 104 or visits closest

to. Fluorescein angiography will be done in the GILA Cohort at baseline (screening visit), week 4, and every 90 days or greater (first visit that occurs \geq 90 days from previous fluorescein angiogram). See Appendix A for schedule of events from screening visit to week 104 and Appendix A.1 for the schedule of events between week 108 and week 156.

End-Point Visits

Subjects will continue to receive study treatments according to the above treatment protocol until week 155. A “Hard End-Point Visit” will occur at week 52, week 104, and week 156. A “Biologic End-Point Visit” will occur 4 weeks after the previous injection near the 12-month time point (week 46 – week 57), 24-month time point (week 92 – week 107). Only best corrected visual acuity and SD-OCT measurements will be recorded at these endpoint visits. No study treatment will be given at these end-point visits, unless the patient has a regular study treatment visit that occurs at these time points.

Fellow eyes not enrolled into a study group that have DME during the course of the study may be treated with standard of care macular laser photocoagulation and/or intravitreal injections of 0.3 mg of ranibizumab at the investigator’s discretion. Ranibizumab will be provided by Genentech for treatment of DME in the fellow eye.

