Subjects will continue to receive study treatments according to the above treatment protocol until week 104. A “Hard End-Point Visit” will occur at week 52, week 104, and week 156. A “Biologic End-Point Visit” will occur 4 weeks after the previous injection near the 12-month time point (week 46 – week 57), 24-month time point (week 92 – week 107), and 36-month time point (week 156). Only best corrected visual acuity and SD-OCT measurements will be recorded at these endpoint visits. No study treatment will be given at these end-point visits, unless the patient has a regular study treatment visit at these time points.

Study eyes which have not met criteria allowing them to extend to at least 6 weeks for two consecutive visits by the week 52 hard endpoint visit will receive a series of three intravitreal injections of ranibizumab 0.3 mg every 4 weeks regardless of OCT measurement, beginning at week 52 if treatment is indicated at that time or the first treatment visit thereafter. The study eye will resume treatment interval determinations based on the pre-specified criteria at the time of the third monthly intravitreal injection.

Fellow eyes not enrolled into a study group and that have DME during the course of the study may be treated with standard of care macular laser photocoagulation and/or intravitreal injections of 0.3 mg of ranibizumab at the Investigator’s discretion. Ranibizumab will be provided by Genetech for treatment of DME in the fellow eye.

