4.5 STUDY ASSESSMENTS

4.5.1 Assessments during the Treatment Period

See the table of events for the exact assessments at each visit.

Vital Signs (All Study Visits)

Vital signs will include measurements of pulse and systolic and diastolic blood pressure while the patient is in a seated position. Vital signs should be taken before injection of study drug.

Ocular Assessments (All Study Visits)

- Best Corrected Visual Acuity Visual function of the study eye and the fellow eye will be assessed using the ETDRS protocol (The Early Treatment Diabetic Retinopathy Study Group, 1985) at 4 meters. After week 104, a new manifest refraction will be performed at week 116, week 128, week 140, and week 156. The pre-existing refraction will be used to test visual acuity at 4 meters in the intervening visits between weeks 104 and week 156.
- IOP measurement- (perform prior to dilating eyes and post intravitreal injection; the method used for a patient must remain consistent throughout the study). IOP may be measured either by TonoPen or applanation tonometry, but the method of measurement must remain consistent for each patient throughout the study.
- Slit lamp examination- Patient's anterior eye structure and ocular adnexa will be examined at each study visit using a slit lamp by the investigator.
- Indirect Ophthalmoscopy- The patient's posterior pole and peripheral retina will be examined by indirect ophthalmoscopy at each study visit pre dose (bilateral) by the investigator

Ocular Imaging

Fundus Photography and Fluorescein Angiography (FA)

The anatomical state of the retinal vasculature of the study eye will be evaluated by funduscopic examination, fundus photography and FA. Fundus photography and Fluorescein angiography will be done in the Monthly and TREX Cohorts at baseline (screening visit) and again at week 12, month 12, month 24, and month 36. Fundus photography and fluorescein angiography will be done in the GILA Cohort at baseline (screening visit), and again at week 4, and then approximately every three months (first visit that occurs > 90 days from previous fluorescein angiogram). See Appendix A. Fluorescein angiography will be used to guide focal laser treatment for all treatment cohorts at week 116, week 128, week 140, and week 152 if laser treatment criteria has been met.

Optical Coherence Tomography (All Study Visits) –

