4.8 STATISTICAL METHODS

4.8.1 Analysis of the Conduct of the Study

The analysis of complete data (36-month treatment period) for the study will be performed when all patients have either completed the visit at month 36 or discontinued early from the study, all data collected from the study are in the database, and the database is locked.

Interim analysis of data from the 12-month period will be performed when all patients have either completed the visit at month 12 or discontinued early from the study. Treatment assignment will be unmasked to the personnel performing the analysis when all data collected through month 12 are in the database and the data have been cleaned and verified. The Peto group sequential procedure ($Z \pm 3.0$ at all interim analyses) will be used to control for the possibility of type I error arising from the 12 month interim analysis.

For the primary objective, power calculations for different margins were undertaken. Familywise alpha of 0.05 was divided equally among three TOST (two one sided test) procedures ($\alpha=0.0167$): (1) comparing TREX vs. GILA in the 60 patients enrolled with bilateral disease, (2) TREX vs. control (total $n=90$, controls $n=30$), and (3) GILA vs. control (total $n=90$, controls $n=30$). A standard deviation of 11 letters was used for the power calculations and based from the RISE/RIDE data for subjects with DME. The power calculations suggests that the minimum boundary of equivalence for TREX vs. GILA that we can demonstrate is ± 7 letters (less than two lines of vision) and ± 9 letters (less than two lines of vision) for TREX and GILA vs. controls. Paired sample t-test will be used to compare TREX vs. GILA and two sample t-test will be used to compare the two groups vs. controls.

Because of the potential for confounding of the effect when comparing the control group (monthly cohort) to the TREX and GILA groups, we will use linear regression modeling with change in ETDRS as outcome

and cohort as main effect controlling for potential confounders (e.g., age, race, sex).

Adverse events, number of injections, and number of office visits will be approached statistically with descriptive analyses with point estimates and confidence limits provided. Exploratory linear, logistic, and time-to-event models will be used to analyze the other secondary outcomes.

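### Between weeks 12 and 104 TREX and GILA eyes are examined less often than Monthly eyes, and the adverse-event summary makes no allowance for it, so short-lived silent findings are under-counted in the treat-and-extend cohorts

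*Combined protocol and SAP*

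**What the plan says.** Incidence and severity of adverse events is the first secondary outcome (2.2, 3.3.2), and safety of treat-and-extend is a stated aim of the trial (section 2). The planned analysis, in 4.8.1, is: "Adverse events, number of injections, and number of office visits will be approached statistically with descriptive analyses with point estimates and confidence limits provided". Section 4.8.2 adds that safety data from all 150 eyes will be summarised.

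Examination frequency depends on the cohort:

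- Monthly (3.1): "subsequent study visits should be scheduled to occur every 28 (± 7) days relative to the date of the first injection".
- TREX and GILA (3.1): the interval can grow in 2-week steps from week 12. In the extension phase, "Treatment is rendered at every visit, no earlier than 7 days before the target date", so the injection interval is also the examination interval. The limits are "The interval between study injections will not exceed 12 weeks in year one of the study" and "The interval between study injections can be extended to, but not more than, 16 weeks in year two of the study".
- Eye examinations are tied to visits (4.5.1): "Slit lamp examination- Patient's anterior eye structure and ocular adnexa will be examined at each study visit using a slit lamp by the investigator". The same section ties vital signs, intraocular pressure and ophthalmoscopy to study visits.
- The additional end-point visits do not fill the gap (4.2, and likewise 3.1): "Only best corrected visual acuity and SD-OCT measurements will be recorded at these endpoint visits".
- From week 104 all three cohorts are seen every 4 weeks.

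**The concern.** Section 5.3 counts adverse events found on examination as well as those volunteered or elicited by questions. Asking about the time since the last visit (5.4.1) should pick up symptomatic events whatever the interval. It cannot pick up a symptom-free finding that has come and gone. For those, the chance of being recorded depends on how often someone looks, and between weeks 12 and 104 that is set by the cohort.

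Increased intraocular pressure and intraocular inflammation are both events of special interest (5.4.2), and both can be silent. A lower incidence in TREX or GILA would mix a real effect of fewer injections with fewer opportunities to find anything, and the planned summary cannot separate the two. For findings of this kind the tilt is always towards treat-and-extend looking safer.

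**Working it through.** The documents give no adverse-event rate, examination count or detection figure, so there is nothing to reproduce. The visit calendars below are built from the rules in 3.1.

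**Calendars.** Monthly is examined at weeks 0, 4, 8, and so on. A TREX or GILA eye is examined at weeks 0, 4, 8 and 12, then extends by 2 weeks per visit until it settles at 6, 8, 12 or 16 weeks, with no interval above 12 weeks set in year 1. This is the fastest path; eyes that start extending later lie closer to Monthly. The 16-week path is 0, 4, 8, 12, 18, 26, 36, 48, 60, 74, 90. An examination at week 104 is credited in every cohort, because the common 4-weekly schedule starts there.

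**Formula.** Assume onset is uniform over weeks 12 to 104 (92 weeks) and the finding is silent and lasts D weeks. In a gap of length g between examinations, onsets in the first g − D weeks are missed. So

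share missed = Σ max(g − D, 0) / 92.

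| Settling interval | Examinations before week 104 | Gaps, weeks 12–104 | Missed, D = 2 | Missed, D = 4 | Missed, D = 8 |
|---|---|---|---|---|---|
| Monthly (4) | 26 | 4 × 23 | 46/92 = 50% | 0% | 0% |
| 6 | 19 | 6 × 15, 2 | 60/92 = 65% | 30/92 = 33% | 0% |
| 8 | 15 | 6, 8 × 10, 6 | 68/92 = 74% | 44/92 = 48% | 0% |
| 12 | 12 | 6, 8, 10, 12 × 5, 8 | 74/92 = 80% | 56/92 = 61% | 22/92 = 24% |
| 16 | 11 | 6, 8, 10, 12, 12, 14, 16, 14 | 76/92 = 83% | 60/92 = 65% | 30/92 = 33% |

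With D of 16 weeks or more, nothing is missed in any row.

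**Effect on a reported percentage.** Assume the same true risk in every cohort, 20% of eyes by week 104, and D = 4. The cumulative rate is −ln(0.8) = 0.223.

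- Week 104: Monthly shows 20.0%. The 16-week eye detects 1 − 60/104 = 0.423 of events and shows 1 − exp(−0.223 × 0.423) = 9.0%.
- Week 156, at the same rate: the cumulative rate is 0.223 × 156/104 = 0.335. Monthly shows 1 − exp(−0.335) = 28.4%. The 16-week eye detects 1 − 60/156 = 0.615 and shows 1 − exp(−0.335 × 0.615) = 18.6%.

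The year of equal visits narrows the gap but does not close it.

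**Sensitivity to the end-point visits.** If full examinations were in fact done at the week 52 and biologic end-point visits, the D = 4 losses would be 24/92, 34/92, 48/92 and 52/92, that is 26%, 37%, 52% and 57%.

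**The case against.** The strongest reply is that the effect is narrow and its size is assumed. Much of that stands.

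- The documents give no durations. A 4-week finding matches the Monthly interval, so Monthly scores perfectly by construction; at 2 weeks Monthly itself misses half.
- Twelve and 16 weeks are ceilings, and eyes that do not extend stay near 4-weekly.
- Pressure rises soon after injection (section 1.5 mentions rises within 60 minutes) are looked for after every injection in every cohort (Appendix B). Fewer of those in TREX or GILA would reflect fewer injections, not less looking.
- The plan envisages 60 patients with both eyes enrolled. Ophthalmoscopy covers both eyes and blood pressure belongs to the patient, so where the two eyes' visits are staggered the gap for these is smaller.
- Section 4.5.1 assigns ocular assessments to all study visits, and the flowchart is a separate document not seen here, so the exact content of the end-point visits cannot be confirmed. The sensitivity figures show that the conclusion does not depend on it.

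It can also be said that injections and office visits are reported in the same sentence of 4.8.1, so a reader would see the imbalance. That helps only in part: office visits may include end-point visits without an eye examination, and nothing links those counts to the adverse-event figures.

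A reader might go further and infer that all cohort adverse-event percentages are biased throughout the trial, or that the plan sets out to claim better safety from raw percentages. The documents support neither. The imbalance is confined to weeks 12 to 104, and persistent findings are found late rather than lost. Section 4.8.1 names no denominator and plans no safety test.

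**Conclusion.** The point holds for transient, silent findings arising in weeks 12 to 104, such as a pressure rise unrelated to an injection, mild inflammation or raised blood pressure. For these the planned between-cohort summary favours TREX and GILA because of the visit schedule alone.

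For an eye taken singly, the loss ranges from nothing (8-week findings at intervals of up to 8 weeks) to about two thirds of 4-week findings at 16-week intervals. These sizes rest on assumed durations, uniform onset and the fastest extension path. Symptomatic events, serious events and persistent findings are little affected. The 36-month totals are diluted by the common schedule after week 104; a 12-month or 24-month summary is not. This is a cheap improvement to the reporting, and it does not invalidate the safety analysis.

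**What to change.** In 4.8.1 and 4.8.2:

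1. Keep the all-visit adverse-event table, and show the number of examinations per eye beside each cohort.
2. Add a table of recorded examination data (pressure before injection, slit-lamp inflammation, blood pressure, fundus findings) restricted to examinations that all cohorts have: weeks 4, 8 and 12; the single examination nearest each of weeks 52 and 104, with its actual timing shown; and the 4-weekly visits after week 104.
3. Report injection-procedure events per injection as well as per eye.
4. Base any between-cohort safety statement on serious adverse events, deaths and the matched-visit table.

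Do not rely on dividing adverse-event reports into symptomatic and examination-only events unless mode of detection is recorded; section 5.3 does not list it among the items described for each event.

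The cost is SAP wording and one or two extra tables from data already collected. No visit or treatment changes. The matched-visit table will hold fewer events and give wider intervals, and in extended eyes the examination nearest week 52 may be some weeks away from it.
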